CoQ10 supplementation significantly increased plasma total and reduced CoQ10 concentrations, % reduced CoQ10, and CoQ10 content in PBMCs in burn patients compared with the placebo group and with the baseline levels prior to the supplementation (Day 0). These data indicate that burn injury decreases CoQ10 levels, which are reversed by CoQ10 supplementation.

CoQ10 supplementation tended to inhibit increased circulating mtDNA levels in burn patients. The pilot data showed that plasma mtDNA levels were significantly greater in burn patients than healthy controls. These results are consistent with previous studies in non-burn major trauma patients²⁹⁻³³. In the placebo group, plasma mtDNA levels tended to increase on Day 3 relative to Day 0 although there was no statistical significance ($p<0.10$). On the other hand, in the CoQ10 group there was a trend toward decreased plasma mtDNA levels on Day 3 relative to Day 0 ($p<0.10$). The Day 3-to-Day 0 ratio of plasma mtDNA levels tended to be lower in the CoQ10 group than the placebo group ($p=0.0765$), but there was no statistical significance possibly owing to the small sample size. Our data suggest that CoQ10 supplementation may protect against burn-induced mitochondrial disintegrity and thereby inhibit an increase in circulating mtDNA levels.

Taken together with previous studies and [name] preliminary data in mice, these findings provide sufficient scientific evidence to test the hypothesis that CoQ10 supplementation prevents MODS by ameliorating mitochondrial dysfunction/disintegrity in burn patients. Collectively, our data warrant a large-scale clinical trial to evaluate the safety and efficacy of CoQ10 supplementation in severely burned patients.

[figure not shown]

Fig. 3. Schematic presentation of the overall hypothesis. Based on previous studies and [name] preclinical and clinical pilot results, we posit that burn injury causes mitochondrial dysfunction/ disintegrity in parallel with CoQ10 deficiency, which in turn induces and/or exacerbates multi-organ dysfunction, leading to worse prognosis. Importantly, pilot clinical data showed that burn injury causes CoQ10 deficiency, which was reversed by CoQ10 supplementation. Moreover, this preliminary data showed that CoQ10 supplementation prevents burn-induced mitochondrial dysfunction/disintegrity, metabolic aberration, oxidative stress and inflammation. These results warrant a clinical trial of CoQ10 supplementation in burn patients.

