Brief study overview: We will conduct a two-arm, prospective, double-blind, randomized, placebo-controlled clinical trial to evaluate the efficacy and safety of reduced form CoQ10 (ubiquinol) supplementation in severely burned adult patients (total n=290) at 15 mature burn centers across North America. Stratified block randomization will take place by site and Revised Baux score. The formula for the Revised Baux score is: Age + Percent Burn (%TBSA) + 17 x (Inhalation Injury, 1 = yes, 0 = no). This formula has been widely adopted for mortality prediction in burn patients^{45,46}. In previous studies, a trend has been shown for a sharp increase in mortality when the Revised Baux score exceeds approximately 110^{45,47,48}. Therefore, patients enrolled in this study will be stratified for randomization into two groups based on the Revised Baux score: (1) less than 110; and (2) equal to or greater than 110. The intervention will consist of a loading dose of reduced form CoQ10 of 1,800 mg/day tid for 4 weeks to be followed by a maintenance dose of 600 mg/day once daily from weeks 5 to 12. The intervention or allocation-controlled placebo will be administered by 72 hours after injury and will continue until 12 weeks after injury or until death or discharge, whichever comes first. Oral tablets (600 mg/tablet) will be administered to CoQ10 subjects who can swallow while a liquid form (100 mg/mL) will be administered to CoQ10 subjects requiring an enteral tube for nutrition. There will be no post-discharge study procedures.

Study investigators, personnel, and centers:

[name] MD, MSCS; UT Southwestern Medical Center/Parkland Memorial Hospital
[name]; Wake Forest University School of Medicine
[name]; University of Texas Medical Branch- Galveston
[name]; The Ohio State University Wexner Medical Center
[name]; University of Alabama-Birmingham Medical Center
[name]; University of Kansas Medical Center
[name]; University of Michigan
[name]; Case Western Reserve University School of Medicine
[name]; Massachusetts General Hospital
[name]; Loyola University Medical Center
[name]; Temple University
[name]; Columbia St. Mary's-Wisconsin
[name]; University of California- Davis
[name]; University of South Florida
[name], MD; University of South Florida
[name]; Hennepin County Medical center

[name], CRA; American Burn Association

[name], MSN; UC Davis, American Burn Association

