Plasma samples for mitochondrial DNA (mtDNA) assays: Plasma samples will be collected on the first 100 subjects enrolled across all centers. These four plasma samples will be collected at four separate time points: 1) at the time of enrollment (and therefore within 72 hours of injury), 2) on post-burn day 7, 3) on post-burn day 14, and 4) on post-burn day 21). Each specimen will be handled in an identical fashion. To remove residual cells, platelets, microparticles, and debris, EDTA-plasma samples will be obtained from whole blood (10 mL) and then the plasma samples will be spun twice at 5,000g⁵⁰. mtDNA will be extracted using the mtDNA extraction kit (Wako Chemicals), and mtDNA levels will be evaluated by real-time PCR using specific primers for mtDNA (forward: 5'-CACTTCCACACAGACATCA-3'; reverse: 5'-TGGTTAGGCTGGTGTAGGG-3')⁵¹. Plasma samples will be stored at -80°C freezer until the measurement. As a standard for the measurement of mtDNA levels, we will use the plasmid vector, in which we subcloned the PCR product from the human PBMC-derived DNA using these primers.

Urine samples for 3-methylhistidine and creatinine assays: 24-hour urine samples will be collected on the first 100 subjects enrolled across all centers. 24-h urine samples will be

collected for three consecutive days at four time points, namely on Days 1-3 (first), 7-9 (second), 14-16 (third), and 21-23 (fourth). Each specimen will be handled in an identical fashion. First, 20 mL of 6N HCl will be added to each container prior to each 24 hour urine collection. 24 hours later, the total 24 hour urine volume will be recorded and that given 24-hour urine specimen will be placed on ice. Once all three 24 hour urine specimens for a given time point are completed, a 20 mL urine sample from each individual 24-hour urine specimen will be collected (2 tubes of 10 mL each) and frozen at -80 degrees C until the measurements. This process will be repeated on each of the three days' collection at the 4 time points. Therefore, each of the first 100 subjects enrolled will generate twelve urine specimens over the four time points.

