3-Methylhistidine concentrations will be quantified by negative chemical ionization gas chromatography mass spectrometry as described in our previous studies^{52,53}. Urinary creatinine concentrations will be measured by a commercial kit. The average of three measurements on the three consecutive days at each time point will be used for statistical analysis to minimize possible day-to-day variations.

STATISTICAL ENDPOINTS AND APPROACH TO DATA ANALYSIS

This two-arm balanced double blind parallel Randomized Clinical Trial (RCT) study will be performed using an intention to treat (ITT) analysis population that includes all randomized patients.

Primary endpoint: The primary endpoint will be the count of the following events. This count will be used to create a composite score ranging from 0 to 6 by assigning 1 to each event regardless of stage, scores and severity that individual subjects encounter from 72 hours after burn injury through 12 weeks or until death or discharge, whichever occurs first:

1. Acute Kidney Injury (AKI) (KDIGO Stages 1 – 3)
2. ARDS (The Berlin ARDS Definition: Mild, Moderate, Severe)
3. Cardiovascular Dysfunction (SOFA Scores 1 – 4)
4. Coagulopathy (SOFA Scores 1 – 4)
5. Liver dysfunction (SOFA Scores 1 – 4)
6. Death (all causes)

We will calculate mean values of the composite sum scores among the study patients in the CoQ10 and placebo arms, and then test their difference by using an independent samples *t*-test if the observed data are evident to follow a normal distribution by Shapiro-Wilk's test. Otherwise, Mann-Whitney U test will be applied and the group specific medians and quartiles will be used as the summary statistics.

AKI: AKI represents the acute loss of kidney function and is associated with a profound and severe increase in morbidity and mortality in burn patients⁵⁴. Early AKI, which occurs less than 3 days post-burn, is usually related to inadequate fluid replacement during the initial resuscitation. AKI can occur later in the hospitalization and late AKI is multifactorial in origin and often associated with sepsis development⁵⁵. For the purposes of this study, we will follow the definitions and classification guidelines set forth in "AKI of Kidney Disease: Improving Global Outcomes (KDIGO)"^{56,57} (**Table 3**). Published in 2012, this guideline has been used in critically ill patients and in combat-injured populations⁵⁸.

Stage	Table 3. AKI (KDIGO)

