Scientific rationale for the observation period: Studies in trauma patients have suggested the organ dysfunction that develops soon after trauma (i.e., during the first 48 -72 h) rapidly resolves in a high proportion of patients and may reflect the reversible derangement of organ function induced by the inciting event or incomplete resuscitation. Thus, it has been proposed that later assessment of organ function (i.e., 3 days after injury) will yield a more accurate definition of multiple organ failure in trauma patients, which is needed to evaluate the relationship between trauma-induced organ dysfunction and prognosis^{71,72}. In the acute phase, particularly the first 72 hours after severe burn injury, organ dysfunction frequently occurs, causing AKI (e.g., oliguria), cardiovascular dysfunction (e.g., hypotension), and coagulopathy (e.g., thrombocytopenia)⁷³. In some cases, the organ dysfunction is transient and the patient may recover during the late-acute or sub-acute phase. In such cases, the recovery from organ dysfunction is associated with relatively good prognosis. In contrast, if the organ dysfunction continues beyond the acute phase or if it occurs or recurs at a later time, the clinical outcome is typically worse. Therefore, we will evaluate the effects of

CoQ10 supplementation on the aforementioned multi-organ dysfunction that patients encounter beginning 72 hours post-burn injury and thereafter.

Secondary endpoints: Secondary endpoints will be the following outcome events observed from 72 hours after burn injury through 12 weeks or until death or discharge (whichever occurs first) and the biochemical measurements in plasma and urine.

1. The six individual binary outcome MODS events and their times of occurrences, (i.e., the constituents of the primary composite score)
2. Weighted composite score of the six constituents
3. Maximum total SOFA score
4. Maximum SOFA score for each organ
5. AUC of total SOFA score (score x days)
6. AUC of SOFA score for each organ (score x days)
7. Delirium (CAM-ICU) (number of days)
8. Length of hospital stay (number of days)
9. Sepsis (Sepsis-3) (number of incidence)
10. Septic Shock (Sepsis-3) (number of incidence)
11. Plasma mitochondrial DNA (4 blood collections)
12. 3-Methylhistidine (3-MH) and creatinine in urine (a biomarker of muscle wasting)

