Data Analysis: For between-arm comparisons of single valued (either measured at once or as an aggregated variable such as AUC over a period) outcomes, we will apply chi-square test if the outcome is binary, and *t*-test or Mann-Whitney *U*-test to continuous outcomes based on the best fit of Shapiro-Wilk's test. The between-arm difference in the distributions of times to the first event and multiple events (of the six constituents) will be examined by using single event time Cox's model and the times to correlated multiple events using Cox's model allowing multivariate frailty, respectively. The incidence rates of each individual event, with- and without differentiating its severity, as a binary outcome will be compared between the two arms by means of longitudinal logistic modeling with generalized estimating equation (GEE)⁸⁴ to allow more than one events per patient. For the repeated measures analysis of the longitudinal plasma mitochondrial DNA and urine 3- methylhistidine (3-MH), we will examine if the mean levels over time are different between the two arms by using longitudinal general linear mixed effects model⁸⁵ which will provide the within group time dependency patterns as a linear effect or more complex form of non-linear patterns which would be able to characterize the time dependent treatment effects over time along with testing for time \times group interaction(s) of those model parameter(s). Total and organ-specific SOFA scores over time will also be examined by this mixed effects models of which the

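### The mtDNA analysis does not use the enrolment sample as a baseline or name the deciding test; if that sample precedes dosing, a four-sample mean estimates only 75% of the post-enrolment effect

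*Combined protocol and SAP*

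**What the plan says.** The Measurement of Biomarkers section states "Plasma samples will be collected on the first 100 subjects enrolled across all centers" and sets four sampling times: "1) at the time of enrollment (and therefore within 72 hours of injury), 2) on post-burn day 7, 3) on post-burn day 14", and finally day 21. The Secondary endpoints list names the endpoint as "Plasma mitochondrial DNA (4 blood collections"; no collection is labelled a baseline.

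The Data Analysis section gives the method: "we will examine if the mean levels over time are different between the two arms by using longitudinal general linear mixed effects" model. The sentence then allows linear or more complex time patterns and adds tests of time by group. Later in that section, all analyses may be extended to adjust for baseline demographic or clinical factors. Enrolment mtDNA is not named among them.

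On timing, the Brief study overview says that study product "will be administered by 72 hours after injury and will continue until 12 weeks after injury". The plan does not say whether the enrolment plasma is drawn before or after the first dose. In the pilot, as described under Preliminary Studies, the Day 0 sample was taken before supplementation, and the reported between-arm comparison was relative to it: "The Day 3-to-Day 0 ratio of plasma mtDNA levels tended to be lower in the CoQ10 group than the placebo group" (p=0.0765).

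**The concern.** A sample taken before treatment cannot carry a treatment effect. If it is averaged with three later samples, the estimated arm difference is pulled toward zero. If it is also not used as a covariate, chance imbalance at enrolment stays in the comparison, and the variance that the enrolment value could explain is not removed.

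The plan names two kinds of test, an overall mean-level comparison and time by group, without ranking them and without fixing the form of time. They estimate different quantities and can disagree, so the answer would depend on a choice made after the data are seen.

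Of the listed endpoints, mtDNA is the one that the plan presents as its measure of systemic mitochondrial disintegrity, which is the proposed mechanism. With about 50 patients per arm, an inefficient or diluted contrast could lead a real effect to be reported as absent.

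**Working it through.** The documents give no effect size, SD, within-patient correlation or power for mtDNA, so there is no figure of the plan's own to reproduce.

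**Inputs from the documents.** Four samples, one at enrolment and three later; 100 subjects; balanced allocation ("This two-arm balanced double blind parallel Randomized Clinical Trial (RCT) study"), hence n = 50 per arm; two-sided 5% level.

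**Assumptions, not in the documents.** Unit SD; equal correlation r between any two samples of a patient (compound symmetry), at 0.3, 0.5 and 0.7; no arm difference at enrolment (sample precedes dosing); complete data; a constant effect d = 0.4 SD on days 7, 14 and 21.

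**Dilution.** The four-sample mean difference is (0 + d7 + d14 + d21)/4 = 0.75 × (d7 + d14 + d21)/3. The factor is 0.75 whatever the shape of the effect, given equal weights and complete data.

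**Variance per patient of each contrast.**
- Four-sample mean: (1 + 3r)/4 = 0.475, 0.625, 0.775; effect 0.75d = 0.30.
- Mean of days 7, 14 and 21, unadjusted: (1 + 2r)/3 = 0.533, 0.667, 0.800; effect 0.40.
- The same mean minus the enrolment value: (4/3)(1 − r) = 0.933, 0.667, 0.400; effect 0.40.
- The same mean adjusted for the enrolment value: (1 + 2r)/3 − r² = 0.443, 0.417, 0.310; effect 0.40.

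For 1-df contrasts, z = effect/√(2 × variance/50) and power = Φ(z − 1.96). Example at r = 0.5: the four-sample mean gives 0.30/√0.025 = 1.90, power 48%; the adjusted mean gives 0.40/√0.01667 = 3.10, power 87%. The 3-df interaction has noncentrality (50/2) × 0.16/[(4/3)(1 − r)] = 4.29, 6.00, 10.00.

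| Contrast | r = 0.3 | r = 0.5 | r = 0.7 |
|---|---|---|---|
| Four-sample mean | 59% | 48% | 40% |
| Time by group, 3 df | 38% | 52% | 76% |
| Later mean minus enrolment, 1 df | 54% | 69% | 89% |
| Later mean, unadjusted | 78% | 69% | 61% |
| Later mean, baseline-adjusted | 85% | 87% | 95% |

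**Equivalent sample size.** Against the adjusted mean, the four-sample mean needs variance/(0.75² × adjusted variance) times the patients: 0.475/(0.5625 × 0.443) = 1.9, then 2.7 and 4.4. The 1-df change contrast needs 0.933/0.443 = 2.1, then 1.6 and 1.3.

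**Shape of the effect.** Let the effect grow as 0.2, 0.4, 0.6 SD over equally spaced visits. The slope difference is 0.2 per visit and the variance of a patient's slope is (1 − r)/5. Then z = 0.2/√(2(1 − r)/250) = 2.67, 3.16, 4.08, and power is 76%, 88%, 98%. The adjusted mean stays at 85%, 87%, 95%, because the average effect is still 0.4.

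**Simulation** (60 runs of 200 patients, r = 0.5, true effect −0.60). The main-effect model averaged −0.45. With assumed missingness of 5%, 20% and 40% on days 7, 14 and 21 it averaged −0.41, so the loss can exceed a quarter. A group-by-post-enrolment interaction gave −0.58, and a model with a common enrolment mean gave −0.59.

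**The case against.** A reader might infer that the trial's mtDNA effect will be diluted by a quarter and the between-patient precision lost. The documents do not support that as a flat statement. The sentence that names mean levels also plans time-by-group tests. These use the enrolment sample as a within-patient reference, remove between-patient variance and are not diluted. Comparing mean levels over time can also be read as comparing mean profiles, and a joint 4-df test of group and interaction would have about 70% power at r = 0.5 under the constant effect. If the effect grows over time, a slope-by-group test does about as well as the adjusted mean, or better, at correlations of 0.5 and 0.7. At low correlation the loss is mostly dilution: at r = 0.2 the four-sample mean has slightly the smaller variance (0.40 against 0.43).

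Two further inferences go too far. One is that the enrolment sample is known to precede dosing; the plan does not say so, and the 0.75 factor needs it. The other is that the pilot's signal appeared only relative to Day 0. No between-arm test of unadjusted levels is reported, so that cannot be known.

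The general promise of baseline adjustment is vague, and it does not clearly exclude enrolment mtDNA. But not being excluded is not the same as being specified. What remains is that the plan assigns the enrolment value no role as a baseline and leaves the deciding test open.

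**Conclusion.** The concern holds as a gap in specification with a measurable cost. If the four-sample mean is the reported contrast and the first sample precedes dosing, it estimates 75% of the mean post-enrolment effect. If time by group is used instead, there is no dilution; under a constant effect, even its best 1-df form needs about 1.3 to 2.1 times the patients of the baseline-adjusted analysis for correlations of 0.7 down to 0.3. All power figures are illustrations that rest on the assumed 0.4 SD effect and compound symmetry, and the ranking against a slope test depends on the shape of the effect.

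The reach is limited: one of twelve secondary endpoints, in the first 100 subjects, with no power claim attached. The change is still worth making, because it uses a value that the trial already collects and fixes the contrast in advance.

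**What to change.** In Measurement of Biomarkers, state that the enrolment plasma sample is drawn before the first study dose.

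In Data Analysis, model mtDNA at days 7, 14 and 21 with enrolment mtDNA as a covariate. Alternatively, model all four samples with the arms constrained to a common enrolment mean, which keeps patients who lack that sample. Name the between-arm difference averaged over days 7, 14 and 21 as the decisive contrast, with time by group as supporting. A log scale is optional and not part of this point.

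The cost is protocol and SAP wording, with no added patients or samples. It should be settled before unblinding.

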Scientific rationale for the clinical secondary endpoints: To comprehensively evaluate the effects of CoQ10 supplementation on dysfunction of organs and systems, we will examine total and individual scores of multiple organs/systems. Severity of multiple organ dysfunction is associated with the morbidity and mortality of burn victims. We will, therefore, evaluate weighted composite score of the six events that constitute the primary endpoint, where stages 1, 2 and 3 of AKI, and mild, moderate and severe ARDS are counted as score 1, 2 and 3, respectively. Regarding cardiovascular dysfunction, coagulopathy and liver dysfunction, we will use the SOFA scores (**Table 5**) for the weighted composite score. Moreover, over and above the maximum severity of organ dysfunction, its duration also affects the clinical trajectory of severely burned patients. Therefore, to take both severity and duration of organ dysfunction into account, we will analyze the area under the curve (AUC) for the SOFA score as previously described⁷⁴.

Our preclinical and pilot clinical studies suggest that CoQ10 supplementation may prevent the development and/or exacerbation of mitochondrial dysfunction/disintegrity and multi-organ dysfunction in burn victims. However, it is possible that CoQ10 supplementation may exert beneficial effects in the recovery phase as well as acute and subacute phases. We will, therefore, investigate the time-dependent effects of CoQ10 supplementation longitudinally.

Delirium, a common complication and significant clinical issue in burn patients, is associated with long-term outcome⁷⁵. [name] preliminary data showed in mice that mitochondrial dysfunction in the central nervous system plays a critical role in surgery/anesthesia-induced delirium⁷⁶. However, the effect of CoQ10 on delirium has not yet been studied in any disease. CAM-ICU will be used to assess delirium⁷⁷.

Sepsis and septic shock are major causes of mortality in burn patients. [name] preliminary study showed in mice that CoQ10 supplementation improved bacterial clearance and survival of septic mice and prevented inflammation organ inflammation (e.g., heart, liver, kidney). For the diagnosis of sepsis and septic shock, we will use the Third

International Consensus Definitions for Sepsis and Septic Shock (Sepsis-3) that was issued in 2016^{78,79}.

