particular interest is to test if the improvement in the longitudinal mean SOFA scores is greater during certain time window. All analyses will also be extended to adjust for the influencing effects of any baseline demographic and/or clinical indications. Missing data may be unavoidable. Because the informed consent from many study enrollees will be obtained through the family members (i.e., surrogates), a small portion (up to 2% attrition rate) of the enrolled patients may voluntarily withdraw from the study. Before final analysis, we will check the missing data pattern of the outcomes first. If there are systematic differences in missing data patterns between the study groups and/or patient characteristics (e.g., burn type), we will take into account such problems in the analysis. The longitudinal mixed effects modeling will provide unbiased and consistent estimates of the effects provided that the missing data mechanism is ‘missing at random’ (MAR). If necessary, multiple-imputation will be applied to all endpoints analyses. All statistical tests will be two-sided and will adopt a 5% significance level.

Sample size calculation: The sample size of 290 study patients for this study is determined to achieve an adequate statistical power at a 5% Type-1 error rate for the primary endpoint analysis by the following statistical calculations. We first estimated the expected means and variances of the composite scores (assuming the six individual events are independent) for the Control and CoQ10 treatment arms under the assumption depicted in **Table 6** via 1000 repeated simulated data sets ($n = 5000$ each), instead of calculating them algebraically.

Each simulation run calculated the means and variances of the two arms, and the resulting average means (and variances) over 1000 simulations were 2.43 (1.04) in the placebo arm and 1.94 (1.05) in CoQ10 arm respectively. Based on the assumption about the event incidence rates and the estimated means and variances of the composite scores from the simulated data sets, the calculated required sample size per treatment arm (using PASS¹¹⁰) to detect such a difference (i.e., 20% reduction in the overall events) with 80% power at a 5% Type-1 error rate using 2-sided independent samples t-test was 142 per arm.

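### The SOFA trajectory analysis tests an undefined time window at an unadjusted 5%, and no global time-by-arm test has to be passed first

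*Combined protocol and SAP*

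**What the plan says.** The relevant text is in the Data Analysis paragraph. It first describes a longitudinal mixed model for plasma mitochondrial DNA and urinary 3-methylhistidine. The time effect in that model is left open: "within group time dependency patterns as a linear effect or more complex form of non-linear patterns". Interactions between time and group are to be tested.

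The same model is then extended to SOFA, for the total and for each organ. What the plan singles out there is this: "particular interest is to test if the improvement in the longitudinal mean SOFA scores is greater during certain time window". No limits, length or number of windows follow.

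The paragraph closes with "All statistical tests will be two-sided and will adopt a 5% significance level". No adjustment for multiple tests is stated.

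The rationale for the clinical secondary endpoints comes nearest to naming windows. It says that "it is possible that CoQ10 supplementation may exert beneficial effects in the recovery phase as well as acute and subacute phases" and that the investigators will therefore "investigate the time-dependent effects of CoQ10 supplementation longitudinally". These phases have no day limits. The listed SOFA secondary endpoints are the maximum and the AUC, total and per organ. The window test is not on that list.

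**The concern.** A test of one window cannot be run until someone names the window. If it is named after the arm-specific curves have been seen, the window with the widest separation is the natural choice, and a nominal 5% test of it no longer has a 5% error rate. If instead several windows are tested and any of them may be reported, the same problem arises without anyone having looked first.

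This is a choice within one analysis of one score. Adjusting across the twelve listed secondary endpoints would not deal with it. At stake is a statement such as a benefit of CoQ10 on organ function in one phase of recovery, which could be reported at p<0.05 with much weaker support than that implies.

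**Working it through.** **Inputs from the plan.** Two-sided level 0.05 for every test; follow-up from 72 h to 12 weeks, death or discharge; total SOFA plus organ scores, with SOFA described as covering six organ systems, so up to seven scores.

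**Inputs assumed.** The number of windows K and the correlation between window-specific test statistics. The documents give neither, so ranges are shown.

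**1. The plan's own figure.** One window fixed in advance: 1 − 0.95¹ = 5.0%. The stated level is right in that case.

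**2. K independent windows, best one reported.** The false-positive rate is 1 − 0.95^K:
- K=2: 9.8%
- K=3: 14.3%
- K=4: 18.5%
- K=6: 26.5%
- K=12: 46.0%

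**3. K correlated windows.** Windows on the same patients are correlated, which lowers these figures. Under no effect, draw (z₁,…,z_K) from a multivariate normal with mean 0 and unit variances, and count the share of draws with max|z| > 1.96. With complete data the sample size does not matter here. Results from 200,000 draws, for the arm difference within each window:

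| K | Correlation | Decaying with distance | Equal for all pairs |
|---|---|---|---|
| 3 | 0.5 | 12.9% | 12.5% |
| 3 | 0.7 | 11.5% | 10.9% |
| 3 | 0.9 | 8.8% | 8.4% |
| 4 | 0.5 | 16.5% | 15.6% |
| 4 | 0.7 | 14.2% | 13.1% |
| 12 | 0.5 | 41% | 32% |
| 12 | 0.7 | 35% | 23% |
| 12 | 0.9 | 21% | 13% |

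The range of roughly 9–41% runs from three highly correlated windows to twelve weekly windows with correlation 0.5 that decays with distance. It is not a bound. Two windows with correlation 0.9 give 7%. Free choice of start and end among 12 weekly steps, comparing change between the two points, gives 65–73%.

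**4. Three concrete windows fixed in advance.** Take 72 h to day 14, days 15–28 and weeks 5–12. Assume a between-patient share of variance of 0.3–0.5 and a serial correlation of 0.5–0.7 between successive scores. With daily scores the correlations between window means are 0.61–0.89 and the rate is 8.9–11.3%. With weekly scores they are 0.48–0.81 and the rate is 10.4–12.1%. Together with the 0.5 row of the table, this is about 9–13%. Defining the windows is therefore not enough if each is then tested at 5%.

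**5. Window against the other windows.** If a greater improvement in one window is read as that window against the average of the rest, the rates are 12% for K=3, 15–17% for K=4 and 32–45% for K=12.

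**6. With a global test first.** If the window-versus-rest contrasts are interpreted only after a significant time-by-arm interaction on K−1 degrees of freedom, the rate is 4.1–5.1% for K=2 to 12.

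**7. Several scores.** All figures above are for one score. Seven independent scores with a single window each would give 1 − 0.95⁷ = 30.2%. This is an upper reference value, because the scores are correlated and the total contains the organ scores.

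**The case against.** The strongest reply is that the plan already holds the protection. SOFA goes into the same mixed model for which time-by-group interactions are tested, and such an interaction asks whether the effect differs over time without choosing a window. Phases are named in the endpoint rationale, and the dosing change at four weeks offers a natural boundary, so windows could be fixed before unblinding. This stands in part: a valid analysis is within reach. But the plan neither makes the interaction a condition for a window claim nor gives the phases day limits.

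A reader might infer that the investigators intend to pick the window from the data, or that this is the only way to run the test. The documents support neither. They are silent on how the window is chosen, and the interaction test is an alternative.

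A reader might also take a single percentage as the error rate of this test. The documents do not support that either, because the figure follows from assumed window counts and correlations. The calculations in steps 2–6 also assume complete follow-up, whereas SOFA observation ends at death or discharge. Simulated discharge gave similar rates, but the figures remain illustrations.

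Finally, the analysis is supportive, and the rationale introduces it tentatively. That limits its importance. It is not labelled exploratory, however: it is called a test of particular interest, and the 5% level applies to it.

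**Conclusion.** The concern holds in a limited form. The window is undefined, the level is an unadjusted 5%, and no global test has to be passed first. If the best of about 3 to 12 windows is reported, the false-positive rate for one SOFA score is roughly 9–41% under the assumed correlations; three windows fixed in advance and each tested at 5% still give about 9–13%. Apart from two windows each compared with the other, which is a single contrast tested at 5%, every multi-window scenario examined without a gate exceeds 5%, but the exact size cannot be derived from the documents.

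A reader might extend this to the trial's main conclusion. That does not follow: the primary composite and the maximum and AUC SOFA endpoints involve no choice of window. The plan should be changed on this point, but the trial's main result does not depend on it.

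**What to change.** Before unblinding, add to the Data Analysis section:

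- **Windows by post-burn day, from the plan's own landmarks.** For example, 72 h to day 14 (the plan treats two weeks as the usual time for MODS to develop), days 15–28 (up to the four-week dosing change) and weeks 5–12. Say whether the clock starts at injury or first dose, since these can differ by up to 72 hours. Other limits would serve as well if fixed in advance.
- **One global arm-by-window interaction for total SOFA at 5%.** Interpret a single window only if that test is significant. A benefit that is constant over time is still captured by the AUC of total SOFA.
- **Labels.** Organ-level windows and any unplanned window are exploratory.
- **The late window.** State that it includes only patients still alive and in hospital. Entry requires an anticipated stay of only two weeks or more, and mean stay in the pilot was about 22 days, though with smaller burns. The late contrast therefore compares groups selected after randomization. It should be called descriptive, or be accompanied by a sensitivity analysis for death and discharge.

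The cost is a few sentences and no extra data. The downside is that an effect in an unforeseen window can be described but not claimed.
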